The median survival of a patient with brain metastases is approximately 1 month if untreated and 2 months with steroid treatment alone. Thus, a large proportion of patients, if untreated, will likely die a neurologic death. For patients that are treated with WBRT, additional prognostic information is provided by the Radiation Therapy Oncology Group's (RTOG) recursive partitioning analysis (RPA), which divided patients into three classes based on age, performance status, and systemic disease control. RPA class I patients (under 65 years of age with good performance status and well-controlled systemic disease) have a median survival of approximately 7 months, whereas RPA class III patients (any patient with a Karnofsky performance status of 70 or worse) have a median survival of only 2 months[1, 2]. As most patients unfortunately do not live beyond these expectations, WBRT is very effective at quickly controlling CNS disease and preventing rapid neurologic decline without having time to manifest any long-term neurologic sequelae. Patchell et al. reported a 48% control (crude, not actuarial, rate) of treated lesions at a median overall survival and follow-up of 15 weeks when radiation is used alone[3].

WBRT has also been studied in conjunction with focal treatments—stereotactic radiosurgery (SRS) or surgical resection—and has been found to improve local control in such situations. In particular, Andrews et al. reported on RTOG 95-08, a phase III trial that randomized 333 patients with 1-3 newly diagnosed brain metastases to either WBRT alone vs WBRT followed by an SRS boost. They did not identify a difference between their treatment arms for their primary endpoint of overall survival. However, they did demonstrate a significant difference of 82% 1-year control of treated lesions in patients treated with WBRT + SRS vs 71% in patients treated with WBRT alone[4]. Aoyama et al. conducted a similar phase III randomized controlled trial of 132 patients with 1-4 brain metastases. They randomized patients to receive WBRT + SRS or SRS alone and demonstrated a similar significant difference in 12-month control of treated lesions of 88.7% for WBRT + SRS vs 72.5% for SRS alone[5]. Chang et al. conducted a phase III randomized controlled trial of 58 patients with 1-3 brain metastases to WBRT + SRS or SRS alone. Although this trial's primary endpoint was neurocognitive function, they also reported on 1-year control of treated lesions: 100% for SRS + WBRT vs 67% for SRS alone[6]. In summary, these three randomized trials all demonstrated a significant improvement with combined modality therapy over single modality therapy in terms of treated lesion control, but no difference in overall survival on initial analysis (see below for discussion of secondary analysis).

Once appropriately managed in the manner described above, patients with brain metastases usually die from non-neurologic causes. In a competing risk analysis, the 6-month and 12-month incidence rates of CNS death were 20.6% and 21.6% after WBRT plus salvage radiosurgery as necessary. In that same study, the incidence of non-CNS death was 34.4%

and 35.0%, respectively[7]. Systemic disease is generally considered the main determinant of patient outcome once brain disease is appropriately treated. With more recent advances in cancer therapy in all disciplines, patients are now living longer, even with brain disease. This observation is often represented in a disease-specific graded prognostic assessment (ds-GPA, see Appendix 1), which is divided by histology and dependent on varying combinations of age, performance status, extracranial disease, number of brain metastases, and receptor or gene statuses. Notably, breast cancer patients with good prognostic factors may live as long as a median of 25.3 months even after the development of brain metastases[8-12]. The original ds-GPA data for non-small cell lung cancer (NSCLC) was updated in 2016, which identified EGFR or ALK alterations as prognostic specifically in adenocarcinoma. In addition, survival times for each subcategory was overall improved as well, likely reflecting the impact of better therapies[13].

Furthermore, there is emerging retrospective evidence that certain subgroups of favorable patients may derive an overall survival benefit with WBRT. In particular, Aoyama et al. reported on a secondary analysis of their JROSG 99-1 clinical of SRS with or without WBRT discussed above. Patients with NSCLC were poststratified by the ds-GPA score, and patients with a ds-GPA score of 2.5 to 4.0 were felt to be favorable. Median overall survival in this favorable subgroup was 16.7 months vs 10.6 months in patients receiving WBRT + SRS vs SRS alone, respectively[14]. Similarly, Sperduto et al. performed a secondary analysis of RTOG 95-08 (also discussed previously) evaluating patients with all histologies but breast (insufficient data) poststratified by ds-GPA. This analysis demonstrated that patients with GPA 3.5 to 4.0 had better OS with WBRT + SRS vs WBRT alone, at a median overall survival of 21.0 months vs 10.3 months, respectively. This analysis was upheld regardless of the number of brain metastases, albeit with small total numbers of patients analyzed[12].

The current standard of care in the management of brain metastasis is well-defined by the National Comprehensive Cancer Network (NCCN) guidelines[15]. In patients with 3 or less brain metastases, patients with uncontrolled primary disease are recommended to have WBRT alone or best supportive care. In patients with stable systemic disease or with reasonable treatment options to achieve such, surgical resection is recommended if possible, followed by radiation therapy to the resection cavity (SRS alone, WBRT alone, or a combination). Patients with unresectable disease are recommended to have WBRT and/or SRS. Patients with more than 3 metastases are recommended to have WBRT or SRS. There is also emerging evidence from Yamamoto et al. in a prospective observational study that the volume of brain disease is more representative of disease burden than the number of metastases[16].

1.2. Neurocognitive considerations in the context of WBRT.

As survival times lengthen in patients with brain metastases, the risks of medium- to long-term neurocognitive decline (which is a well-described toxicity of whole brain radiation therapy) must be addressed. Early cognitive decline after WBRT is primarily manifested as a decline in short-term memory within 1 to 4 months. Long-term decline and more permanent adverse effects include cognitive deterioration in other domains (e.g., attention) as well as possible cerebellar dysfunction[17]. Long-term survivors may be at risk of radiation-induced dementia, although this is typically seen primarily with higher dose per fraction regimens (even if the total dose is not high)[18].

Several approaches have been explored to decrease the risk of neurocognitive toxicity secondary to WBRT. Presently, many radiation oncologists favor the use of SRS alone followed by close observation and salvage SRS as needed, with WBRT reserved for salvage treatment of diffuse intracranial recurrence. This approach is supported by the previously described studies of SRS +/- WBRT, which did not identify any overall survival advantage to SRS + WBRT despite the presence of a significant local and distant brain control benefit. Furthermore, these trials suggested that SRS alone was associated with improved neurocognitive outcomes. However, the SRS-alone approach has the disadvantage of higher in-brain distant failure rates at 12 months of 55-63.7% with SRS alone vs 27-41.5% when WBRT + SRS is used[5, 6]. A pooled analysis by Tsao et al. again demonstrated a statistically significant local and in-brain distant control benefit favoring WBRT + SRS over SRS alone, with hazard ratios of 2.61 and 2.15, respectively[19].

Another strategy to decrease the risk of neurocognitive toxicity due to whole brain radiation therapy was studied by RTOG 09-33, a phase II trial investigating the role of hippocampal avoidance in WBRT. The hippocampus is crucial for memory formation and hippocampal radiation is thought to contribute significantly to memory impairment in patients undergoing brain radiation. Thus, Gondi et al. demonstrated that in RTOG 09-33 there was a significant improvement in Hopkins Verbal Learning Test-Revised Delayed Recall at 4 months. While these results were significant and encouraging, criticisms of this study include the fact that only 42 of 113 patients were analyzable (likely due to patient dropout from death), the estimated 5% chance of failure at the hippocampal region, the comparison against historical controls, and the use of only one time point for assessment[20].

Brown et al. reported on RTOG 06-14 in which patients were randomized to WBRT with or without the addition of memantine, a drug thought to be protective against neurocognitive decline. Neurocognitive function was measured by multiple subtests of the Hopkins Verbal Learning Test – Revised (HVLT-R). The trial demonstrated a trend toward improved cognitive function with the addition of memantine that was not statistically significant, possibly due to the fact that only 149 of 508 patients were analyzable at the prespecified analysis point of 24 weeks[21].

Finally, whole brain dose de-escalation is another promising approach and is the strategy we propose to use in the present study. The concept of dose de-escalation in the brain is not novel. In fact, the standard dose for prophylactic intracranial irradiation (PCI) is 25 Gy in 10 fractions, lower than the 30 Gy in 10 fractions for standard WBRT. The goal for PCI is to eliminate microscopic disease, albeit in a relatively radiosensitive tumor histology[22]. Further, RTOG 09-33 as mentioned above essentially dose de-escalated in the hippocampal region alone with good effect. This trial allowed dose to 100% of the hippocampus to be 9 to 10 Gy, and the maximal hippocampal dose to be 16 to 17 Gy[23].

1.3. The concept of simultaneous integrated boost (SIB) with WBRT.

In the context of the current paradigm of SRS alone with close follow-up, reliable patients are ideally identified as early as possible if and when any new lesions should arise. Nonetheless, there is always the risk of patients not returning for follow-up and/or any new lesions causing unsalvageable neurologic deficit[19, 24]. Furthermore, this method is also primarily validated for treating 4 or fewer brain metastases. Patients with more than 4 brain

metastases are most often treated with WBRT with hippocampal avoidance when available, but often insurance denies payment when attempted off trial.

Recently, there have been some data suggesting that WBRT with SIB using intensity-modulated radiation therapy (IMRT) is technically feasible and can potentially approximate WBRT + SRS. Several dosimetric studies have demonstrated that WBRT with simultaneous integrated boosts up to 70.8 Gy is feasible using both reverse and forward planning on both helical tomotherapy and LINAC-based systems[25-28]. In particular, one study discusses that 30 Gy WBRT and 60 Gy SIB provides a similar biologically equivalent dose to the treated lesions as compared to a radiosurgical boost of 18 Gy after 30 Gy WBRT as was studied in RTOG 95-08[29]. Their calculations were based on the concept of the universal survival curve and single fraction equivalent dose[30].

Further, several institutions have reported on retrospective data demonstrating reasonable efficacy in terms of patient outcomes and intracranial disease control across a variety of platforms and dosing regimens. Weber et al. noted a 6 month in-brain progression-free survival of 77.9%[31]. Zhou et al. noted a 1 year local brain failure rate of 13.8% and distant brain failure rate of 19.2%[32]. Kim et al. noted a 1 year intracranial control rate of 67%[33]. Oehlke et al. noted a 1 year in-brain progression-free survival of 45.3%[34]. At a median follow-up of 4 months, Vargo et al. noted local brain control to be 72% and distant brain control to be 92%[35]. Tomita et al. noted a 1 year local control rate of 69%[36]. In addition, the phase I trial by Rodrigues et al. briefly discussed previously was not powered to assess control but did note a crude 75% overall brain control rate. Specifically, it noted that of 32 assessable patients, 4 had local progression, 2 had in-brain distant progression, and 4 had both[29].

The concept of WBRT + SIB has only been explored in a very limited sense as described above. Depending on the modality of SRS utilized (i.e., Gamma Knife vs LINAC-based), the incidental whole brain dose may start to approach therapeutic doses as increasing number of brain metastases and thus increasing number of beams or isocenters generate more low dose scatter throughout the brain. There have been some retrospective studies exploring SRS treatment to more than 4 lesions that attempt to evaluate the dose to normal brain. One study by Takahashi et al. suggests that when patients are treated with LINAC-based radiosurgery to more than 8 targets, 50% of the normal brain received a dose of 8.7 Gy or higher[37]. Studies by Xue et al. and Yamamoto et al. suggests that the normal brain dose is closer to a median of 3-5 Gy with radiosurgery to multiple targets, albeit on the Gamma Knife platform[16, 38]. Although conflicting, these studies do demonstrate a relatively small but potentially significant normal brain dose when treating with radiosurgery.

The theoretical advantage of WBRT + SIB over current, more standard therapeutic options includes maximizing the benefit of combined modality therapy (namely, better treated lesion and distant brain control over single modality treatment) as well as combining two disparate treatment courses into one course, all with little added morbidity or time on the patient's part. The role of WBRT in providing an overall survival benefit in patients with favorable prognosis is also being re-explored given the secondary analyses described in section 1.1.

1.4. The assessment of neurocognitive function.

Neurocognitive function assessment has been an area of investigation in brain radiation for many years, and particularly since the 2000s after the FDA indicated that neurocognitive outcomes were acceptable end points for clinical trials in the late 1990s. Meyers and Brown reviewed this topic in 2006 and identify 6 main characteristics that a neurocognitive test battery should have in order to be useful in the clinical trials setting[39].

1. Brevity – on the order of 30 minutes or less – is important to reduce patient and clinician burden.
2. Repeatability is necessary to account for improvement from pure repetition and learning the test (i.e., practice effects).
3. Psychometric robustness in terms of validity, reliability, and population norming is important to detect true changes in function rather than those related to situational or chance factors.
4. Sensitivity to changes in cognitive function in order to detect fine changes.
5. Standardization and ease of administration.
6. Ease of completion by patients, including those with significant cognitive deficits, which would reduce selection bias for those that will do well.

To assess neurocognitive function, we will use the Hopkins Verbal Learning Test Revised (HVLT-R.) The HVLT-R has been used and validated in multiple trials related to brain metastasis. In particular, RTOG 00-18 was a feasibility study of neurocognitive function testing on a national scale[40]. They demonstrated compliance rate for testing before treatment, at treatment completion, and at 1 month was $\geq 95\%$, $\geq 84\%$, and $\geq 70\%$, respectively. Several tests were assessed, including the HVLT. Meyer et al. reported on a phase III randomized trial investigating the benefit of motexafin gadolinium on the survival and neurologic and neurocognitive outcomes of patients receiving WBRT for brain metastases[41]. Of the several neurocognitive tools used, the HVLT for immediate recall, delayed recall, and recognition were incorporated. This study did not demonstrate any difference in time to neurocognitive function. It did show that compliance with testing was 87-98% at baseline and 77-87% at 6 months.

For the present protocol, we will be using the HVLT-R. The HVLT-R is a 12 noun list with 4 words each from 1 or 3 semantic categories that are learned over the course of three learning trials. After 20-25 minutes, delayed recall and recognition are also assessed. This test is estimated to take 5-10 minutes with a 25 minute delay in the middle to allow for appropriate assessment of delayed recall. The focus of this test is on assessing verbal learning and memory. In situations where in-person visits are discouraged or not allowed (e.g. the COVID-10/SARS-Co-V2 pandemic), we may opt to administer the HVLT-R via a telehealth visit.

A baseline neurocognitive function assessment will be performed at the time of CT simulation. The follow-up time points chosen include 3-, 6-, and 12-months post-treatment. Patients will be seen at 1-month post-treatment as well but will not be assessed for neurocognitive function at that time. Given our inclusion/exclusion criteria of a life expectancy of at least 6 months per ds-GPA (see Appendix 1 for more detail), we anticipate that a large proportion of our patients will be assessed at time points up to 6 months. We acknowledge the possibility that a small but significant proportion of our patients may die before the 12-month assessment but remain interested in attempting to examine long-term

cognitive outcomes. Neurocognitive assessment will be conducted by trained and certified research nurses or associates, these assessments may be conducted either in person or via remote modalities

1.5. The assessment of quality of life.

Quality of life is an important metric, particularly as the goal of therapies move away from curative intent toward palliative intent and life expectancies are limited. We will assess quality of life in our cohort of patients using the Functional Assessment of Cancer Therapy with Brain Subscale (FACT-Br) tool.

FACT-Br is a self-administered questionnaire assessing multiple dimensions of a person's daily life, including physical, social, emotional, and functional well-being, as well as specific questions related to neurocognitive quality of life that might be affected by cancer therapy to the brain. A total of 50 questions arranged on 3 pages are present, all using a 5-point Likert scale. This tool is available free-of-charge to academic institutions with registration of the study at www.facit.org, and with the agreement to provide the organization with a copy of any publications that result from the use of this questionnaire.

Our quality of life assessment will follow the same schedule as noted above for neurocognitive assessment. This may be completed in clinic or electronically or physically mailed to patient and completed survey returned to clinic.

1.6. Summary and specific aim.

Based on the summarized data above, we are interested in exploring the role of WBRT with SIB in the management of brain metastases. The concept is that WBRT with SIB would be expected to maximize both local and in-brain distant control as has already been shown in studies exploring WBRT with SRS boost. However, by itself WBRT with SIB does not address the concern over neurocognitive outcomes. **Therefore, we hypothesize that there is a lower WBRT dose threshold that will maintain acceptable in-brain distant control, particularly in the setting of a SIB to gross lesions to maintain treated lesion control.** In addition, lower overall brain dose (including lower hippocampal dose without specific hippocampal avoidance) may potentially improve neurocognitive function. We are also interested in evaluating treated lesion control, overall survival, neurocognitive sequelae of therapy, quality of life, performance status, and adverse effects of therapy. Biomarker identification for potential correlative circulating tumor DNA and microRNA is an exploratory endpoint to generate data for future prospective evaluation.

Ideally, this method would combine the benefit of combined modality therapy in preventing neurologic decline due to an uncontrolled gross brain lesion (as demonstrated in SRS + WBRT) with the benefit of lower total brain dose in improving neurocognitive outcomes (as demonstrated by RTOG 09-33 and hippocampal avoidance). More realistically, we would find a balance between neurocognitive deficit from WBRT itself vs neurocognitive deficit from new and/or progressing lesions. We would also be able to treat more than 4 brain metastases as WBRT is already used in the setting of a significant burden of CNS disease. This method could also be an alternative at centers where Gamma Knife or radiosurgery is not available. Further, there is the added time and resource usage benefit of condensing two procedures (WBRT and SRS) into one procedure (WBRT + SIB). There is also a theoretical dosimetric advantage of taking into account both the whole brain aspect

and the boost aspect of the treatment in one planning session. Lastly, some patients are not able to tolerate the head frame placement that is required for Gamma Knife therapy, and WBRT + SIB would provide such patients with an additional treatment option.

OBJECTIVES

2.1. Primary Objective

Evaluate two de-escalated whole brain radiation dose levels (in the setting of simultaneous integrated boost to gross lesions) with respect to in-brain distant control for brain metastases, defined as an in-brain failure rate outside of the planning target volume at 6 months of < 20%.

2.2. Secondary Objectives

1. Evaluate treated lesion control at 6 months for brain metastases in the setting of a predetermined total biologically effective SIB dose as determined by radiographic progression within the planning target volume with fusion and overlay of follow-up MRIs.
2. Evaluate overall survival at 6 months for brain metastases in the setting of WBRT with SIB.
3. Evaluate changes in neurocognitive function after WBRT with SIB in the following domains: verbal learning and memory as assessed by the HVLT-R.
4. Evaluate changes in health-related quality of life as assessed by the Functional Assessment of Cancer Therapy with Brain Subscale (FACT-Br) after WBRT-SIB for brain metastases.
5. Evaluate changes in performance status as assessed by the Karnofsky Performance Status tool (see Appendix 2) after WBRT-SIB for brain metastases.
6. Evaluate adverse events after WBRT-SIB for brain metastases according to current CTCAE criteria.

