3.2. Secondary Outcome Measures

1. Treated lesion control, defined as an actuarial 6-month rate of any new, recurrent, or progressing (as defined by RANO criteria, see Appendix 3) tumor within the planning target volume on any post-treatment MRI by 6 months. Follow-up MRIs will be fused with the planning scan for this assessment.
2. Overall survival, defined as an actuarial 6-month rate of patients still alive regardless of disease status at 6 months.
3. Neurocognitive function change, defined as the change from baseline neurocognitive testing scores at a 6-month time point with respect to the HVLT-R.
4. Health-related quality of life change, defined as the change from baseline quality of life assessment at a 6-month time point with respect to the FACT-Br tool.
5. Performance status change, defined as the change from baseline performance status at a 6-month time point with respect to the KPS clinical assessment tool.
6. Incidence of early and late adverse effects as defined by the CTCAE, at any time point during the study follow-up.

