4.2. Exclusion Criteria

1. Previous radiation to the brain, including WBRT or brain radiosurgery.
2. Life expectancy < 6 months (as estimated per the current ds-GPA, see Appendix 1 for details).
3. For histologies not included in the ds-GPA publications or otherwise noted online at brainmetgpa.com, the PI will use either published or validated data, or the PI's best clinical judgment to determine the patient's expected survival.
4. Inability to comply with treatment per investigator discretion.
5. Inability to complete neurocognitive assessments per investigator discretion.

Of note, tumor lesion number is not an inclusion or exclusion criteria as we are using volume-based criteria instead.

5. **STUDY DESIGN**

This trial is a pilot, Phase 2, sequential two-cohort study designed to test two de-escalated WBRT dose levels and assess their ability to maintain acceptable in-brain distant control. The WBRT dose would decrease as we move forward in the study, both in terms of absolute value and EQD2 (i.e., equivalent dose in 2 Gray fractions, as determined by the linear quadratic radiobiological model). The absolute value of the SIB dose will change with each dose level because the number of fractions delivered will depend on the WBRT dose. As such, the SIB dose will be manipulated such that the EQD2 will remain essentially equivalent despite the difference in the number of fractions delivered. This design will ensure that the only variable is the change in WBRT dose.

The next phase of investigation would depend upon the outcome of this study. If we are able to demonstrate that both treatment levels in this study meet our primary endpoint, it would suggest that we have not yet found the lowest acceptable WBRT dose. As such, we would then consider a similar study in which we lower the WBRT dose further. If we do find the lowest acceptable WBRT dose, we envision that the next step would be an appropriately powered equivalency trial comparing that lowest acceptable WBRT dose with SIB vs standard WBRT alone vs standard radiosurgery alone. Outcomes in this trial would include standard efficacy outcomes, survival outcomes, and neurocognitive outcomes.

6. **PATIENT REGISTRATION**

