10.6. Patient Characteristics and Significant Protocol Violations

Baseline subject characteristics will be tabulated, such as demographics (age, race, gender), and disease characteristics (KPS score). Significant protocol violations such as with respect to eligibility criteria and cohort will be tabulated.

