10.8. Analysis of Primary Objectives

All analyses will be done by cohort. For the primary objective, the number of patients who have in-brain distant failure in the evaluable patients will be summarized and exact binomial 95% confidence intervals will be determined.

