10.9. Analysis of Secondary Objectives

For Local Control and Overall Survival, the median and the corresponding two-sided 95% confidence intervals will be calculated using the Kaplan-Meier method. Estimates and 95% confidence intervals will also be provided for 6 and 12 months.

For quality of life measures and neurocognitive assessments, appropriate subscales will be calculated at each time point, along with change from baseline to 3, 6, and 12 months, and summarized descriptively by cohort. Baseline Karnofsky Performance Status and change from baseline to 1, 3, 6, and 12 months will also be summarized and reported by cohort. Summary descriptive statistics only (i.e. no inferential statistics) will be used for all measures except for HVLT-R. An analysis will be done for HVLT-R to use the change from baseline results and compare them to the results generated from the RTOG 0933 study. Wilcoxon Rank Sum Tests will be used for this comparison.

All safety data will be listed. For the treatment-emergent AEs, namely AEs started or worsened during the on-treatment period, the incidence will be summarized by system organ class and/or preferred term, severity based on CTCAE grades, type of adverse event and the relation to the study drug. Deaths reportable as SAEs and non-fatal serious adverse events will be listed by and tabulated by type of adverse event. This will be done with the safety set.

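### Overall survival is planned as a crude Kaplan-Meier estimate with no prognostic reference, and by default in a population that leaves out early deaths

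*Combined protocol and SAP*

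**What the plan says.** Section 2.2, item 2, sets the objective: "Evaluate overall survival at 6 months for brain metastases in the setting of WBRT with SIB". Section 3.2 gives the outcome as "Overall survival, defined as an actuarial 6-month rate of patients still alive regardless of disease status at 6 months". Section 10.9 gives the method: "For Local Control and Overall Survival, the median and the corresponding two-sided 95% confidence intervals will be calculated using the Kaplan-Meier method", and adds "Estimates and 95% confidence intervals will also be provided for 6 and 12 months". Section 10.8 states "All analyses will be done by cohort". No stratum, covariate or benchmark is named for survival. The Cox models in 10.10 are for the biomarkers.

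Section 10.9 does not say which patients enter the survival analysis; it names the safety set only for adverse events. The default is therefore 10.4.3, which reserves efficacy analysis for treated patients who were evaluated for the primary endpoint at the 6-month scan. Section 10.5 adds that patients who die before 6 months without confirmed in-brain distant failure are replaced if possible. Neither 3.2 nor 10.9 gives a time origin for survival.

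Prognosis is assessed at entry. Section 4.2 excludes "Life expectancy < 6 months (as estimated per the current ds-GPA, see Appendix 1 for details". For histologies that ds-GPA does not cover, the next item uses published or validated data or the principal investigator's judgment. Section 1.1 describes ds-GPA as divided by histology and "dependent on varying combinations of age, performance status, extracranial disease, number of brain metastases", plus receptor or gene status. In 10.6 the only disease characteristic given for the baseline table is "disease characteristics (KPS score", as an example in an open list.

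**The concern.** Any solid tumor is eligible (4.1), there is no control arm or randomization (5, 10.2), and each cohort has about 20 evaluable patients (10.5). A crude 6-month survival of, say, 70% could be better or worse than these patients would have been expected to achieve, and the planned output cannot show which. Yet an expected survival has already been worked out for most patients to apply the eligibility rule. The protocol treats that score as strongly prognostic: both secondary analyses that Section 1.1 cites for a survival benefit were post-stratified by it.

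The population matters more. A survival estimate restricted to patients who reached a 6-month scan largely conditions on the event that it is meant to measure. At stake is whether the reported survival figure can be interpreted at all. No decision rule depends on it.

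**Working it through.** **1. The plan's own precision figure.** The only one is for the primary endpoint: 90% half-widths of 17.0%, 14.7% and 13.2% at a 20% failure rate (10.5). With 1.645 × √(0.2 × 0.8 / n), n = 15, 20 and 25 give 16.99%, 14.71% and 13.16%, so it reproduces. None is stated for overall survival.

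**2. Sampling error of survival.** For n = 20 and a 6-month survival of 73% (the middle of the classes in step 3), the 95% half-width is 1.96 × √(0.73 × 0.27 / 20) = 0.195, or about ±19 points. The exact 95% interval for 14 of 20 alive is 46% to 88%.

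**3. Expected survival by class.** Inputs are the Table 16-2 medians (Appendix 1). Those of at least 6 months number 18: 6.9, 6.9, 7.3, 7.7, 8.8, 9.4, 9.8, 11.3, 12.8, 13.2, 13.5, 13.7, 14.8, 14.8, 15.1, 25.3, 26.5 and 46.8 months. Assuming exponential survival, S(t) = 0.5^(t/median):

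- Lowest class: S(6) = 0.5^(6/6.9) = 54.7%; S(12) = 30%.
- Highest class: S(6) = 0.5^(6/46.8) = 91.5%; S(12) = 84%.
- Medians from 6.9 to 15.1 months (15 of 18 classes): S(6) from 54.7% to 75.9%.
- Only three classes lie above that, at 84.8%, 85.5% and 91.5%.
- Equal weight on all 18 classes: 70%.

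The documents do not state a survival shape. With the same medians, a Weibull shape of 0.8 gives 54% to 87.5% at 6 months, and a shape of 1.3 gives 56% to 95%.

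**4. Expected 6-month survival of a whole cohort.** Illustrative mixes of 20 patients, exponential, no treatment effect:

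| Mix (medians in months) | Expected S(6) |
|---|---|
| 18 at 6.9, 2 at 46.8 | 58% |
| 10 at 7.7, 10 at 13.7 | 66% |
| 10 at 6.9, 10 at 46.8 | 73% |
| 10 at 13.7, 10 at 26.5 | 80% |

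**5. Difference between two cohorts.** Two cohorts of 20 were drawn at random from the 18 classes with equal weights (an assumption). The difference in expected 6-month survival has SD 3.3 points (95% range about ±6.5); the observed difference has SD 14.4 points. Chance case mix therefore explains (3.3 / 14.4)² ≈ 5% of the variance.

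**6. Effect of the analysis population.** Suppose 20 are treated and 14 are alive at 6 months, so survival is 14/20 = 70%. If the six who died are not counted as evaluated at the 6-month scan, the estimate is 14/14 = 100%. If two of the six had confirmed in-brain distant failure first and were counted as evaluated (an assumption), it is 14/16 = 87.5%. Replacements who must also reach the scan do not remove the bias.

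**7. Precision of an observed/expected ratio.** With 6 deaths observed and 6 expected (30% of 20), the exact Poisson 95% interval is about 0.37 to 2.18.

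**The case against.** Survival here is a descriptive secondary outcome in a pilot. It has no test, no benchmark and no part in the stopping or interim rules, which use only in-brain distant failure. The baseline list in 10.6 is open, and 10.1 allows further exploratory analysis, so tabulating histology or ds-GPA is already permitted. An observed/expected ratio as wide as 0.37 to 2.18 cannot separate halved from doubled mortality. It would also absorb differences between trial patients and the published series. All of this stands, and it limits the remedy to a descriptive reference.

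Three stronger readings are tempting, and the documents do not support them:

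- A reader might infer that every patient has a ds-GPA class. Section 4.2 provides otherwise for histologies outside the index.
- A reader might infer from the 55% to 91% range that the survival result mainly reflects who was enrolled. That range is between single classes, and a cohort reaches either end only if all its patients sit there. The top value is one class. Moving from two-thirds 7-month-median and one-third 25-month-median patients to the reverse shifts expected survival from 2/3 × 0.55 + 1/3 × 0.85 = 65% to 75%. Those 10 points compare with a sampling half-width of about ±19.
- A reader might infer that a survival difference between cohorts would be mainly case mix. By chance alone it would not be (step 5), and no such comparison is planned. A systematic shift is possible, because Cohort B opens only after Cohort A's 6-month scans and Appendix 1 requires the web version of the index current at each registration. Nothing in the documents shows that one will occur.

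Nor does Section 5 say that this survival estimate feeds the next trial; it only lists survival among that trial's outcomes.

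**Conclusion.** The concern holds for the absolute level of overall survival, on two counts. The larger is the population: read as written, 10.4.3 and 10.5 would push 6-month survival toward 100% whatever the prognostic mix. This rests on survival counting as an efficacy analysis, which is the natural reading because 10.9 names no other set for it. The second is the missing reference. Expected 6-month survival among eligible classes runs from about 55% to 91%, mostly 55% to 76%, so a crude figure from an uncontrolled cohort says little by itself. That range rests on exponential survival and on Table 16-2, which the web version at registration supersedes. Neither count affects the primary endpoint's decision rules, and the conclusion does not extend to differences between the cohorts.

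**What to change.** In 10.9, state that overall survival is estimated by Kaplan-Meier in all treated patients (the safety population of 10.4.2), from the start of treatment. Patients who die before the 6-month scan are included, whether or not they are replaced for the primary endpoint.

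Beside each cohort's estimate, report descriptively the mean expected 6- and 12-month survival, computed from each patient's ds-GPA median as obtained at registration. State the assumed survival shape. List patients without a ds-GPA class separately, with their observed survival. Label any observed/expected ratio as imprecise and show its exact interval.

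In 10.6, name ds-GPA class and histology, by cohort, in support.

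The cost is SAP wording and one table. The score is already obtained for eligibility where ds-GPA applies, so the main task is to record it. The downside is that the expected figures rest on published medians and an assumed survival shape. They serve as a reference, not a test, and the text should say so.
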